Elastomeric power chains are resilient and latex-free orthodontic materials. They are made up of elastic material and consist of many connected rings. Each ring is engaged in a bracket to apply a force of 175-300 gm.

Plaque Index:¹⁷ (Annexure C)

Plaque index is a grading system used to assess the amount of plaque present at the gingival margins and helps in assessing oral health. It consists of four grades including, Grade 0, 1, 2 and 3. The increase in grade indicates the increased amount of plaque along the gingiva.

Gingival Index:²¹ (Annexure D)

Gingival index is a grading system that is used to assess the health of the gingiva. It consists of four grades including, Grade 0, 1, 2 and 3. The increase in grade indicates the compromised gingival health of the teeth.

Root Resorption:²²

Root resorption is a decrease in root length and width due to an inflammatory process. In orthodontics, during tooth movement, areas of necrosis develop called hyalinized areas, which result in root resorption. Periapical radiographs will be taken to assess the amount of root resorption by determining the length of the tooth from the cusp tip to the root apex.

Retraction Rate:¹⁶

The retraction rate of canine will be the distance travelled divided by the time interval needed for closure of spaces. It will be noted at four-time intervals i.e at the start of the canine retraction (T_0), after first month (T_1), second month (T_2) and third month follow-up (T_3).

Split-mouth Study:

A randomized controlled trial in which intervention and control are randomly allocated to the different quadrants in the oral cavity. In our study, Ni-Ti closed-coil springs and elastomeric power chains will be randomly allocated to the right and left quadrants of maxillary and mandibular arches.

MATERIAL & METHODS:

Study Design: A single center open labelled parallel split-mouth randomized controlled trialSettings: Dental clinics, Department of Surgery, The Aga Khan University Hospital, Karachi, Pakistan

Study Duration: One year after ethical review committee (ERC) approval **Sampling Technique:** Non-probability consecutive sampling

SAMPLE SIZE:

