The sample size was calculated using standard estimate where n = 8(CV2) /(PC2) [1+(1-PC)2] where PC is the proportionate change in means (PC = $(\mu 0 - \mu 1)/\mu 0$) and CV is the coefficient of variation (CV = $\sigma 0/\mu 0 = \sigma 1/\mu 1$). The study required a minimum sample size of 33 (N) patients in each group. With an inflation of 40% for an estimated loss to follow up/non-response rate, we will be including 46 (N) participants in this study, to achieve 80% power and to detect at least a 39% change in mean canine retraction rate values of 3.88 ± 2.66 mm and 5.45 ± 1.53 mm, with

elastomeric power chains and Ni-Ti closed-coil springs, respectively⁸ and 68% or less change in coefficient of variation at two-sided 5% level of significance.

SAMPLE SELECTION:

Inclusion Criteria:

- Patients aged between 13 40 years
- Patients undergoing fixed orthodontic treatment
- Patients requiring all first premolars extraction as part of orthodontic treatment
- Patients with all permanent teeth present and erupted (except for second and third molars)
- All patients who will sign the informed consent/assent form

Exclusion Criteria:

- Patients with systemic diseases that can affect tooth movements
- Patients with uncontrolled periodontal disease
- Patients with craniofacial syndromes
- Pregnant or lactating mothers
- Patients with bracket failures greater than three times per bracket during the study
- Patients on medications that can affect tooth movements
- Patients with Nickel allergy

DATA COLLECTION PROCEDURE:

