Randomization will be used in the study to allot one of the two treatment methods used for canine retraction to each side of the mouth to minimize bias and to account for individual variability. By randomly assigning different retraction methods to each side of the mouth any individual-specific factors that may affect the treatment outcomes (oral hygiene habits, masticatory habits) are likely to be equally distributed across the treatment group. Block randomization will be performed to code the type of retraction method in this trial and to determine the sequence of its administration to each participant. This will be controlled by a research faculty member of the Section of Dentistry at AKUH.

Sequence Generation:

In this two-armed study, four-blocks, each with a block size of six-possible allocation sequences for treatment arms will be generated.

(1) AABB, (2) BBAA, (3) ABAB, (4) BABA, (5) ABBA, (6) BAAB

The blocks to be utilized and their order will be determined by the research faculty member using sealed envelopeTM online software.²⁴

Allocation Sequence Concealment:

After fulfilling the inclusion criteria and obtaining consent, the patient will be recruited in the study. During the recruitment of the participants in the trial, the sealed envelope for a participant will be opened by the enrolling team member and will be allotted an intervention according to the ascending order sequence already generated by the principal investigator who is also a biostatistician.

Enrollment:

After obtaining approval from the ERC (AKUH), each participant fulfilling the inclusion criteria for the study and consenting to participate in the trial will be assigned a participant ID.

Blinding:

The study investigators, patients recruited, and assessors will not be blinded during the trial. All the measurements will be recorded by the co-investigator on the study proforma (Annexure H).

POSSIBLE RISKS OR BENEFITS:

Nickel is a known allergen, though people with nickel allergy tolerate stainless steel brackets and wires quite satisfactorily.²⁵ However, in case of any adverse events such as allergic reaction to Ni-Ti closed-coil spring such as contact dermatitis, rash, bumps, redness or irritation of the skin or mucosa, its use will be stopped, and patient will be excluded from the study.

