Adverse events will be reported to ERC within a week and any serious adverse event will be reported to the Department of surgery, sponsors, CTU, DRC, and ERC within 24 hours. All emergency side effects will be managed in the emergency department and the Department of Surgery will bear the charges.

STUDY GROUPS:

The patients will be screened using the inclusion and exclusion criteria by the co-investigator. Measurements for the canine root resorption, retraction rate, plaque accumulation and gingival health will be taken at T_0 , T_1 , T_2 and T_3 .

Intervention: Ni-Ti closed-coil springs **Control:** Elastomeric power chains

The participants will receive routine instructions for oral hygiene maintenance and care of the appliance verbally.

MATERIAL STORAGE:

Ni-ti closed-coil springs and Elastomeric power chains will be stored at room temperature at the Department of Surgery, Dental inventory.

DATA ANALYSIS:

Data will be entered and analyzed in SPSS for Windows (version 23.0, SPSS Inc. Chicago). Frequencies and proportions will be reported for categorical variables, such as gender. Shapiro-Wilk test will be used to check the normality of the data. Descriptive statistics, such as means and standard deviations for normally distributed or median and interquartile range (IQR) for non-normally distributed data will be reported for all baseline clinical factors. Paired t-test will be used for the pairwise comparison. For the two groups the mean/median scores for retraction rate, root resorption, gingival health and plague accumulation between the two groups will be assessed using Independent t-test for normally distributed data and Man-Whitney U test for non-normally distributed data. A *p*-value ≤ 0.05 at 95% confidence interval will be considered as statistically significant.

On achieving 50% of the sample size, an interim analysis will be run, if the results show that the given intervention is successful in significantly improving the rate of canine retraction in patients then further trial will be stopped and all the participants will be given the intervention.

FINANCE:

Departmental funds from the Department of Surgery and intramural grants will be applied for.

PUBLISHING POLICY/PLAN:

For publication the data will be utilized, and it could be presented in either national or worldwide forums.

DATA CONFIDENTIALITY:

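### Two rules drop randomised patients for events that can only happen after allocation; the one tied to the Ni-Ti spring can flatter Ni-Ti gingival health, probably by a small amount

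*Protocol*

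**What the plan says.** The Exclusion Criteria under Sample Selection include "Patients with bracket failures greater than three times per bracket during the study". The other entries in that list describe conditions that exist at enrolment, among them "Patients with Nickel allergy".

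Possible Risks or Benefits adds a second rule. It applies "in case of any adverse events such as allergic reaction to Ni-Ti closed-coil spring", lists skin and mucosal signs including reddening and irritation, and concludes that "its use will be stopped, and patient will be excluded from the study". No matching rule is given for the elastomeric chain. The same section provides that "Adverse events will be reported to ERC within a week".

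On timing, Allocation Sequence Concealment says that during recruitment "the sealed envelope for a participant will be opened by the enrolling team member". On design, the split-mouth definition has the two devices "randomly allocated to the right and left quadrants of maxillary and mandibular arches", so each patient wears both devices in both arches. On masking: "The study investigators, patients recruited, and assessors will not be blinded during the trial".

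Gingival health is a secondary objective. Annexure D grades it from 0 to 3, higher being worse, on erythema, inflammation and bleeding.

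**The concern.** Eligibility criteria should use only what is known before allocation. A count of bracket failures during the study does not exist at that point, so the criterion can act only by removing a patient already randomised. The reaction rule does the same.

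The reaction rule matters more for bias, for four reasons:

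- It depends on how one of the two compared devices behaved.
- Its signs partly overlap the features that the gingival index scores.
- Those who judge whether a reaction occurred know which side carries the spring.
- The words introducing the trigger are open-ended, so screening out nickel allergy need not cover every case.

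The rule removes the patient and not just the spring, so both sides leave together and the two sides stay equal in number. The bias is therefore not an imbalance in numbers. It is a selection of patients by how their Ni-Ti side reacted. Patients with high Ni-Ti gingival scores leave, and the remaining average favours Ni-Ti. Reporting reactions to the ethics committee makes them visible but does not return the patient to the comparison.

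For bracket failure, the primary retraction comparison would be biased only if failures differed by device. The protocol does not say whether they do, so neither direction nor size can be given.

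**Working it through.** **Order of events.** The envelope is opened at recruitment. Failures during the study and reactions to a fitted spring come later. Both rules therefore act after allocation.

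**Denominators.** The plan's sample-size formula with CV = 0.68 and PC = 0.39 gives 8 × 0.68² / 0.39² × [1 + (1 − 0.39)²] = 33.4, against the stated 33. Inflation by 40% gives 33 × 1.4 = 46.2, against the stated 46. I use N = 46 (all randomised) and N = 33 (the stated minimum, if losses use up the inflation).

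**Formula.** Let D be the mean Ni-Ti minus chain gingival difference, at the visit where the reaction is scored, in the k patients who would be excluded. Let d be the same difference in the other N − k.

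- Mean in all patients: [kD + (N − k)d] / N
- Mean after exclusion: d
- Shift in favour of Ni-Ti: k(D − d) / N

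**Assumed inputs.** The protocol gives no event rates. I take k = 1 or 3, and D − d from 0 to 2 grades.

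| N | k | D − d = 0 | D − d = 1 | D − d = 2 |
|---|---|---|---|---|
| 46 | 1 | 0 | 0.022 | 0.043 |
| 46 | 3 | 0 | 0.065 | 0.130 |
| 33 | 1 | 0 | 0.030 | 0.061 |
| 33 | 3 | 0 | 0.091 | 0.182 |

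**Reactions needed for a shift of 0.1 grade.** This is k = 0.1N / (D − d). With N = 46 it is 4.6 patients if D − d = 1 and 2.3 if D − d = 2. With N = 33 it is 3.3 and 1.65. In both cases that is 10% or 5% of patients.

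**Data lost.** Each exclusion removes 4 canines, or 2 side pairs. Three exclusions remove 12 of 46 × 4 = 184 (6.5%), or 12 of 33 × 4 = 132 (9.1%).

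**Retraction.** Without failure rates by device, no shift can be calculated for the primary outcome.

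**The case against.** The strongest reply is that exclusion from the study may mean only an end to participation, with data already recorded kept. The protocol nowhere says these data are discarded, and analysis populations are commonly left to the SAP, which is not at hand. On that reading, if the event visit is kept, the shift at that visit disappears. What remains is that later visits are lost, and a SAP cannot recover measurements never taken. That reading also fits poorly with a criterion placed in the eligibility list. The point is about two rules the protocol states, not about an analysis set it omits.

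A second reply is that a patient who proves nickel-allergic was never in the intended population, so removal merely restores it. This has some force for true allergy. It does not cover irritation that is not allergic, and it does not justify removing patients by how their randomised device performed.

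Several limits on size stand:

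- Skin reactions add nothing to a gingival score, and a reaction on both sides reduces D.
- Scoring takes place only at T0 to T3, so a reaction between visits may never be graded.
- Once the spring is stopped, D − d may be near 0.
- Against all 46 randomised, the top of the range is 0.13. The 0.18 needs N = 33.

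The 40% inflation does not answer the point. It protects power and does not correct selective loss.

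**Conclusion.** The concern holds. Both rules remove randomised patients for later events, and one is specific to a single device. The bracket-failure line is misplaced whatever its effect, because it cannot be applied at enrolment.

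If excluded patients are left out of the comparison, the reaction rule can favour Ni-Ti on gingival health by 0 to 0.06 grade for one exclusion and 0 to 0.18 for three, on a 0 to 3 scale. These figures rest on assumed numbers of reactions and an assumed excess of 0 to 2 grades, and they apply to the visit at which the reaction is scored. The effect is probably small because known nickel allergy is screened out, and it is 0 if reactions spare the gingiva. That it is small is a judgement, since no event rate is given. No effect on retraction is shown. It should be corrected because the remedy is cheap and the selection depends on one of the compared devices.

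**What to change.** 1. Take the bracket-failure line out of the Exclusion Criteria, so that they cover only conditions known before allocation. If it is kept as an in-study rule, place it elsewhere and state that it does not remove the patient from the analysis.
2. In Possible Risks or Benefits, separate stopping the device from leaving the study. Whether and when to stop the device is a clinical matter and is not addressed here.
3. State that patients with either event stay in the analysis as randomised, that measurements up to and including the event visit are used, and that later scheduled measurements are collected where possible.
4. Report bracket failures and reactions by device. A sensitivity analysis without these patients may be added. Handling of missing later visits can be left to the SAP.

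The cost is new wording in two places and recording failures and reactions by side. The data become slightly more variable. Visits after a spring is stopped no longer reflect its wear, which may dilute the difference between devices, including in retraction. The later scheduled measurements include periapical radiographs, which is one reason to ask for them only where possible.

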After obtaining an approval from the Ethical Review Committee and taking informed consent and informed assent from the parents and child respectively, (Annexure E, F and G), these patients will be recruited in the study as participants. Patients visiting the orthodontic clinic at the Aga Khan University Hospital Karachi will be included in this study. Detailed information regarding the study will be provided to the participants and they will be given the choice to either accept or refuse their inclusion in the study. After the extraction of all first premolars under local anesthesia, 0.018" stainless steel archwires will be inserted in the maxillary and mandibular arches. For canine retraction, Ni-Ti closed-coil springs and elastomeric power chains will be randomly allocated to the right and left quadrants of both arches. Radiographic measurement (root resorption) and clinical measurements (canine retraction, plaque accumulation and gingival health) will be

recorded at four points in time. First, at the start of the canine retraction (T_0), after first month (T_1), second month (T_2) and third month follow-up (T_3). Canine retraction rate will be recorded by using a 100 mm marked scale.¹⁶ Data will be collected on an organized study proforma (Annexure H).

Ethical Considerations:

This study will be carried out as per the guidelines of the World Medical Association's Declaration of Helsinki.²³ and the principles of Good Clinical Practice (GCP). Any modifications in the protocol will be re-submitted to the ERC. The study will be conducted in compliance with regulations and a copy of the final study protocol will be submitted to ERC. All the recorded data of patients will remain confidential. Access will be provided to no one except the investigators. Participants' names and identities will remain undisclosed; however, data may be seen by ERC or any local regulatory body. Data will be saved for 7 years as per GCP and institutional guidelines.

Randomization:

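### Devices are randomised to right and left within each patient, but the between-device tests use neither the patient pairing nor the side: unbiased, slightly conservative, and almost free to improve.

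*Protocol*

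**What the plan says.** The Randomization section uses random allocation to "allot one of the two treatment methods used for canine retraction to each side of the mouth", with the stated aim of minimising bias and allowing for differences between individuals. Data Collection Procedure adds that "Ni-Ti closed-coil springs and elastomeric power chains will be randomly allocated to the right and left quadrants of both arches". Each of the six sequences listed under Sequence Generation holds two A and two B, so the allocation is balanced within blocks. On the habits it has in mind, the Randomization section states that "any individual-specific factors that may affect the treatment outcomes (oral hygiene habits, masticatory habits) are likely to be equally distributed across the treatment group".

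Data Analysis then names the tests. One sentence reads "Paired t-test will be used for the pairwise comparison", without saying what is paired with what. The next assigns the comparison of the two groups on retraction rate, root resorption, gingival health and plaque to the "Independent t-test for normally distributed data and Man-Whitney U test for non-normally distributed data". No named test contains a term for side. The protocol reports no left-right difference for any outcome, and no within-patient correlation.

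**The concern.** Once the devices are allotted to sides in balanced blocks, side is part of the design, much as period is in a crossover trial. Suppose right and left differ on average by L, whatever the device. In a patient with the spring on the right, L is added to the spring-minus-chain difference; in a patient with it on the left, L is subtracted. Balance makes these contributions cancel in the mean. They do not cancel in the observed spread, so the standard error is larger than the design requires. The independent t-test and the Mann-Whitney U test lose more, because they also treat the two sides of one mouth as if they came from different people.

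At stake is precision, not validity: power on the primary outcome, and on plaque and gingival scores if those have a consistent left-right pattern.

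**Working it through.** **Inputs from the protocol (Sample Size):** chain 3.88 (SD 2.66) mm; spring 5.45 (SD 1.53) mm; difference 5.45 − 3.88 = 1.57 mm; 33 patients before inflation; 80% power; two-sided 5%.

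**Assumed, because the protocol gives neither:** within-patient correlation ρ from 0 to 0.7; average right-minus-left difference L of 0.25, 0.5 or 1.0 mm.

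**1. The plan's own figure.** n = 8 × CV²/PC² × [1 + (1 − PC)²] with CV 0.68 and PC 0.39 gives 8 × 0.4624/0.1521 × 1.3721 = 33.4, which agrees with the stated 33. Then 33 × 1.4 = 46.2, which agrees with 46. (PC has to be entered as a positive number for this to match.)

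**2. Variance of a within-patient difference.**

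- With side modelled: V = 2.66² + 1.53² − 2ρ(2.66)(1.53) = 9.417 − 8.140ρ.
- With side ignored: V + L².

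**3. Power of a paired comparison, 33 patients.** Noncentral t with noncentrality √33 × 1.57/√variance; 32 degrees of freedom without side, 31 with side.

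| ρ | V (mm²) | No side term, L = 0.25 | L = 0.5 | L = 1.0 | With side term |
|---|---|---|---|---|---|
| 0 | 9.42 | 81.1% | 80.3% | 77.3% | 81.2% |
| 0.3 | 6.97 | 90.9% | 90.2% | 87.2% | 91.1% |
| 0.5 | 5.35 | 96.4% | 95.9% | 93.5% | 96.5% |
| 0.7 | 3.72 | 99.4% | 99.2% | 98.1% | 99.5% |

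The loss is 0.3 to 0.9 points at 0.5 mm and 1.4 to 3.9 points at 1.0 mm. The added variance, L²/V, is 2.7% to 6.7% and 10.6% to 26.9% respectively. The formula treats L as random noise and so slightly overstates the loss under exact balance. In simulation at ρ = 0.5, L = 1.0 mm and 32 patients, power was 93.6% without side and 95.5% with it.

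**4. The test actually assigned to the device comparison.** The independent t-test works from 2.66² + 1.53² = 9.417, and each arm carries ±L/2. An unmodelled side difference therefore adds L²/2 to that sum: 0.125/9.417 = 1.3% at 0.5 mm and 0.5/9.417 = 5.3% at 1.0 mm. Ignoring the pairing costs far more: 9.417/V is 1.35 at ρ = 0.3, 1.76 at 0.5 and 2.53 at 0.7, even with L = 0.

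**5. Simulation** (8,000 replicates, 32 patients, ρ = 0.5):

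| L (mm) | Type I error: independent t | paired t | paired t with side | Power: independent t | paired t | paired t with side |
|---|---|---|---|---|---|---|
| 0 | 1.0% | 5.1% | 5.1% | 87.0% | 96.2% | 96.2% |
| 0.5 | 1.0% | 4.7% | 5.2% | 87.7% | 95.9% | 96.3% |
| 1.0 | 1.3% | 3.5% | 5.4% | 85.5% | 93.6% | 95.5% |

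The device estimate showed no bias in any setting.

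**The case against.** The strongest objection is that the protocol never says the named habits act by side. It calls them individual-specific, and a fixed side term removes only a left-right difference shared across patients. If the favoured chewing side or the brushing pattern varies from patient to patient, a side term leaves that variation in place. This stands: an average left-right difference is a possibility, not something the document reports.

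A reader might also infer that the quoted sentence is wrong about bias. It is not. Random, balanced allocation to sides does equalise such factors between devices in expectation, and the estimate is unbiased without a side term.

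A reader might further infer a serious loss of power. Let δ be L divided by the SD of the within-patient device difference, and start from exactly 80% power with 33 patients (a standardised device effect of 0.503). Power falls to 78%, 71% and 61% at δ = 0.25, 0.5 and 0.75. But 0.5/0.503 is about 1 and 0.75/0.503 about 1.5, so the two lower figures need a systematic side difference as large as the device effect, or half as large again. Nothing in the protocol supports that.

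Finally, a covariate of this kind can be left to a statistical analysis plan, which is not shown. That argues for low priority. It does not remove the point, because the protocol itself assigns the device comparison to tests that ignore both pairing and side. The separate mention of a paired t-test does not settle the matter: its comparison is undefined, and it would restore the pairing but not the side.

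**Conclusion.** The point holds as a small loss of precision. The design randomises side within patient, and the tests assigned to the device comparison use neither feature. For retraction rate, the cost of leaving side out of a paired analysis is at most about 1 point of power at a 0.5 mm average side difference and 1 to 4 points at 1.0 mm. A 1.0 mm difference would be about two thirds of the 1.57 mm device effect (1.0/1.57 = 0.64). These figures rest on the protocol's standard deviations, 33 patients and an assumed correlation of 0 to 0.7. Nothing can be sized for plaque and gingival scores.

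The error is in the conservative direction, and the documents support no claim of bias. The larger gain from the same change is the pairing: about 87% against 96% power at 32 patients if the correlation is 0.5.

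**What to change.** In Data Analysis, replace the independent t-test and Mann-Whitney U test for the device comparison with an analysis of within-patient differences that includes side (right or left) as a fixed factor, for each outcome. One form is a mixed model with patient as random effect and device, side and arch as fixed effects. Because each patient contributes two arches, the model should also let the canines on one side be correlated, or the two arches should be averaged first.

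State whether the spring goes on the same side in both arches; the protocol does not say. If it does, a simple equivalent is to take each patient's right-minus-left difference (arches averaged), compare spring-right with spring-left patients, and halve the contrast to obtain the device effect. A Mann-Whitney U test on those differences is the rank-based counterpart for the 0 to 3 scores.

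The cost is a sentence or two and one degree of freedom. If there is no side effect, 80% power becomes 79.9%. No new data are needed beyond recording which side received which device. Label: free improvement, low priority.

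### The allocation envelope is opened at recruitment and nothing requires T0 to be recorded first, so the zero point of the primary outcome may be read with the device side known

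*Protocol*

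**What the plan says.** **When the allocation is revealed.** The only text that times the opening is in Allocation Sequence Concealment. It begins "After fulfilling the inclusion criteria and obtaining consent, the patient will be recruited in the study", and continues "During the recruitment of the participants in the trial, the sealed envelope for a participant will be opened by the enrolling team member". No measurement is named as a condition.

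**When recruitment happens.** Data Collection Procedure links recruitment to ethics approval and consent or assent: "these patients will be recruited in the study as participants". The extractions may still lie ahead at that point, because the inclusion criterion is a need for them: "Patients requiring all first premolars extraction as part of orthodontic treatment".

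**When T0 happens.** The same section then describes the extractions, the stainless steel archwires and the allocation of devices ("Ni-Ti closed-coil springs and elastomeric power chains will be randomly allocated to the right and left quadrants of both arches"), and only after that the measurements. It lists the measurement times as "First, at the start of the canine retraction (T_0), after first month (T_1), second month (T_2) and third month follow-up (T_3".

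**Who knows and who measures.** Under Blinding: "The study investigators, patients recruited, and assessors will not be blinded during the trial". The co-investigator records all measurements (Blinding) and also screens patients (Study Groups).

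**What depends on T0.** Operational Definitions gives the retraction rate as distance moved over elapsed time, noted at T0 to T3. Data Collection Procedure has it read on a 100 mm marked scale. Study Groups has all four outcomes measured at T0.

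**The concern.** Nothing in the treatment differs between the two sides until the first device is attached. In an open-label trial of two visibly different devices, T0 is therefore the one set of readings that can be taken with the side assignment unknown, without any masking. The plan as written does not secure this.

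The primary outcome needs a zero point, and that zero point is a hand reading. The split-mouth layout gives no protection, because both devices are in the same mouth: a reading that leans one way on the spring side goes straight into the within-patient contrast.

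There is a second, smaller consequence. A patient whose envelope is opened at recruitment and who leaves before retraction starts has been randomised but has no T0 data.

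**Working it through.** **Step 1. Order of events under each section.**

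- Allocation Sequence Concealment, combined with the place of recruitment in Data Collection Procedure: consent → recruitment and envelope → extractions → archwires → T0. Allocation comes before T0.
- Data Collection Procedure alone: consent and recruitment → extractions → archwires → allocation (no time given) → measurements from T0. Allocation is still mentioned before the measurements. A T0 reading taken at the same visit just before allocation is not excluded, but it is not required either.

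The sections place allocation at different points. Under neither is T0 secured before the assignment is revealed, and no sentence keeps the assignment from the person measuring.

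**Step 2. The plan's own figures.** The Sample Size formula, with the stated 39% change and 68% coefficient of variation, gives

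n = 8 × 0.68² / 0.39² × [1 + (1 − 0.39)²] = 24.32 × 1.3721 = 33.4, stated as 33;

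33 × 1.40 = 46.2, stated as 46.

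These are not in dispute here, and the timing of the envelope does not change them. The planned difference from the same section is 5.45 − 3.88 = 1.57 mm.

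**Step 3. What a T0 shift would do.** Let the T0 reading on one side be off by b relative to the other. Distance on each side is the T3 position minus the T0 position, so the difference between sides in T0–T3 distance moves by b, one for one. The mean of the three monthly distances is (T3 − T0)/3, so the same proportion applies there. Monthly intervals tested separately would be affected only in T0–T1.

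**Step 4. Illustrative size.** The documents give no value for b, no reading error for the scale and no within-patient correlation ρ. The following are assumptions: b from 0.1 to 0.5 mm, ρ from 0 to 0.7, a two-sided paired z-test at 5%, and the planning SDs (2.66 and 1.53) taken to apply to the T0–T3 distance.

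- SD of the difference = √(2.66² + 1.53² − 2ρ × 2.66 × 1.53), which is 3.07 at ρ = 0 and 1.93 at ρ = 0.7.
- SE = SD/√n; with n = 33 this is 0.534 and 0.336.
- Chance of a significant result with no true difference = Φ(−1.96 + b/SE) + Φ(−1.96 − b/SE).
- Example: b = 0.5, ρ = 0, n = 33: b/SE = 0.936, so Φ(−1.024) + Φ(−2.896) = 0.153 + 0.002 = 0.155.

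| Assumed b (mm) | b / 1.57 | Type I error, 33 patients | Type I error, 46 patients |
|---|---|---|---|
| 0.1 | 6% | 0.054–0.060 | 0.056–0.064 |
| 0.25 | 16% | 0.075–0.116 | 0.086–0.142 |
| 0.5 | 32% | 0.155–0.319 | 0.197–0.420 |

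The ranges run from ρ = 0 to ρ = 0.7. At 0.1 mm the error rate is close to nominal. At 0.5 mm it is not, and recruiting more patients makes it worse.

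**The case against.** The strongest reply is that the sequence is inferred. No sentence says that the envelope is opened before the extractions, and the only step-by-step account mentions allocation after the archwires. That stands. A reader might infer that every baseline will be taken with the device known; the documents show only that this is allowed.

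Other stronger readings also go further than the text:

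- **That the extractions and archwires are done with the side assignment known.** The operator is not identified, and nothing says the allocation is passed on. The co-investigator who measures is not named as the team member who opens the envelope. The text says that assessors are not blinded, not that they look.
- **That a T0 shift contaminates every later comparison.** Whether the retraction rate is cumulative or monthly is not stated. Data Analysis compares mean or median plaque and gingival scores between groups and states no change from T0, so a comparison of T3 scores would be untouched.
- **That losses before T0 bias the comparison.** Each patient carries both devices, so such a loss removes both sides equally. It costs numbers, not balance. The 40% inflation makes some allowance, and how much of the loss would fall before T0 is not given.
- **That patients could be selected by arm.** Every patient receives both devices, so this does not arise.

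It is also fair to say that T1 to T3 will be read unblinded whatever is done about T0, so the gain is partial.

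The open-label label does not answer the core of the point. It accounts for unmasked readings once the devices are in place, not for an unmasked T0.

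**Conclusion.** The point holds in a limited form. The envelope is timed at recruitment, T0 falls later, the two sections place allocation differently, and nothing requires T0 to be recorded before the side is revealed to unblinded staff. The plan thereby fails to secure an unbiased zero point for its primary outcome, although doing so would be nearly free.

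The size of any bias cannot be derived from the documents. The 6% to 32% of the planned 1.57 mm rests wholly on an assumed shift of 0.1 to 0.5 mm and on a cumulative T0–T3 contrast (or the mean monthly rate). The error rates rest in addition on the assumed correlation and paired test. At the low end the effect is negligible. This is an avoidable weakness that merits a change of wording, not a flaw that invalidates the trial.

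**What to change.** In Allocation Sequence Concealment, replace opening during recruitment with opening at the T0 visit, after all T0 measurements have been entered on the proforma and immediately before the first device is attached. Align Data Collection Procedure so that it gives the same order: T0 recorded, envelope opened, devices attached.

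Consent and the participant ID can stay at recruitment. The sample size stays at 33, inflated to 46. No extra visit or staff is needed, and since every patient receives both devices, both are needed at that visit anyway. The cost is a few sentences of protocol text and handling the sealed envelope chairside.

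The change protects T0 only; T1 to T3 remain unblinded. It has the further benefit that patients who drop out before T0 are not randomised.
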